10.4 DATA SOURCES

This active surveillance is based on existing and newly collected data at selected centers where IPF patients are regularly treated.

Data of the individual patients will be gathered using electronic data capture (EDC) system. The medical records of Group A and B patients will be used to collect the data of covariates as described in [section 10.3.3](#) and all ADRs and SAEs occurring during the duration of the treatment/ 52 weeks, whichever is earlier. This data will be entered into eCRF and reported via NIS AE form as per [section 12.2](#). Group B and C patients will be followed-up according to clinical practice for at least 52 weeks/discontinuation (whichever is earlier) from the start of the treatment, at regular intervals (i.e. approximately every 4 weeks for the first 3 visits and every 12 weeks thereafter till week 52). After the completion of medical examination and observation at the suggested time points, investigator needs to enter data of the registered patients (all ADRs and SAEs) in the EDC system and report via NIS AE form as per [section 12.2](#). Additionally information on certain covariates will be collected at subsequent visits as described in the [section 10.3.3](#). For patients treated with Pirfenidone, only baseline characteristics will be recorded in EDC and these patients will not be followed.

10.5 SAMPLE SIZE

200 IPF patients treated with nintedanib according to approved Indian label (classified as Group A, B and C, see [section 10.1](#)) will be enrolled in this active surveillance program. The sample size of 200 is as per the request from the regulatory agency.

In addition 200 IPF patients who were treated with pirfenidone (classified as Group I, II and III, see [section 10.1](#)) at the same centres and during the same time frame will also be included. The baseline characteristic of these patients will be recorded at visit 1 and they will not be followed.

10.6 DATA MANAGEMENT

Patients' data will be gathered in the EDC system and outsourced to a CRO.

10.7 DATA ANALYSIS

Analyses will be descriptive in nature including means, medians, standard deviation and interquartile range for continuous variables, and frequencies and percentages for binary and categorical variables with the corresponding 95% confidence intervals. For safety outcomes, incidence rates with corresponding 95% confidence intervals will be calculated. The baseline characteristics of 200 pirfenidone treated patients will be used to compare with the patients profile of the Nintedanib users. Whenever patient profiles differ between those treated with nintedanib and pirfenidone, cautious interpretation is required.

Subgroup analysis will be performed according to prior treatment (see [section 10.7.1](#)).

Any patient who meets the following criteria is treated as ineligible for safety analysis:

- Required registration procedure was not followed

10.7.1 Analyses of outcome events

All outcome events are based on reported AE data which will be handled according to BI standards (see the section below). In addition, patients for all analysis will be stratified by (i) no prior IPF treatment (ii) prior Pirfenidone treatment (switch) (iii) other prior treatment used for the management of IPF (switch) (iv) other prior treatment used for the management of IPF (add-on). In case of conflicting results the results of the first strata [(i) no prior IPF treatment] are decisive, because in new users potential bias is the smallest.

Safety:

In general, safety analyses will be descriptive in nature, and will be based on BI standards, and will focus on all ADRs and SAEs.

AEs will be coded using the current version of the Medical Dictionary for Regulatory Activities (MedDRA) and will be based on the concept of treatment emergent AEs. To this end, all AEs occurring between first intake of Nintedanib prescribed at visit 1 and up to 52 weeks/discontinuation will be considered 'treatment emergent'. An AE is considered to be an ADR if either the physician who has reported the AE or the sponsor assesses its causal relationship as 'related'.

The frequency and incidence of ADRs and SAEs will be tabulated by system organ class and preferred term.

No imputation is planned for missing AE data except for missing onset dates which will be handled according to BI standard.

Descriptive statistics will be calculated for laboratory tests, vital signs and physical examination.

10.7.2 Interim analyses

Starting from the date of this amendment, a status report of the active surveillance will be submitted to DCGI annually. No formal interim analysis is required.

10.8 QUALITY CONTROL

It is the responsibility of the investigator to ensure that recorded data is as accurate and complete as possible. Investigator and site staff will be trained on this. Data will be entered directly in to e-CRF by the site staff; and data quality will be ensured by having the process of validation and edit checks in-built in the system.

10.9 LIMITATIONS OF THE RESEARCH METHODS

The scientific objective of this active surveillance is to obtain an estimate of the occurrence of all ADRs and SAEs in IPF patients prescribed Nintedanib per the approved label in the real world setting. For retrospective data, there may be a possibility of missed information on adverse events. For patients followed prospectively, lost to follow up, loss of information and recall bias could impose limitations. Since only the cohort treated with Nintedanib will be followed up, it is impossible to assess the safety of Nintedanib compared to other drugs. The possible selection bias will be minimised by enrolling all patients who have initiated or will initiate nintedanib (Group A, B and C) from the date of commercial availability of drug (23rd January 2017) at selected centres and potential channelling bias will be assessed by recording the baseline characteristics of a comparator group of equal number of patients who have been treated with pirfenidone.

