10. RESEARCH METHODS

10.1 STUDY DESIGN

200 IPF patients treated with nintedanib per the Indian label will be enrolled in this active surveillance program. They are classified into following groups:

- Group A. Patients who started treatment with nintedanib after 23rd January, 2017 and have permanently discontinued the drug (as decided by the investigator) at the time of participation in the active surveillance. Data for these patients will be collected in anonymized manner after getting approval from the Ethics Committees for data collection and sharing.
- Group B. Patients who started treatment with nintedanib after 23rd January, 2017 and are continuing the drug at the time of participation in the active surveillance.
- Group C. Patients who have been newly prescribed nintedanib at the time of participation in the active surveillance.

In addition 200 IPF patients treated with pirfenidone will also be enrolled. They are classified into following groups:

- Group I. Patients who started treatment with pirfenidone after the 23rd January, 2017 and have permanently discontinued the drug (as decided by the investigator) at the time of participation in the active surveillance. Data for these patients will be collected in anonymized manner after getting approval from the Ethics Committees for data collection and sharing.
- Group II. Patients who started treatment with pirfenidone after the 23rd January, 2017 and are continuing the drug at the time of participation in the active surveillance.
- Group III. Patients who have been newly prescribed pirfenidone at the time of participation in the active surveillance.

The medical records at the selected sites will be screened to enroll Group A and B patients in a retrospective manner. Group C patients will be enrolled prospectively. The first patient enrolled at a given site should be in the nintedanib group. Once a patient is enrolled into the nintedanib group, the site team is suggested to enrol the next eligible patient, who has initiated or will be initiating pirfenidone at the same site in the pirfenidone group.

The safety data for nintedanib treated patients will be collected for at least 52 weeks or till the discontinuation of the drug, whichever is earlier. Patients treated with pirfenidone will not be followed.

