10.2.2.2 Registration period

There is no specific time frame for the enrolment period. It will end as soon as 200 patients are enrolled.

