10.2.2.3 Patient registration method

In accordance with the inclusion & exclusion criteria, 200 IPF patients who have initiated or will initiate nintedanib (classified as Group A, B and C, see [section 10.1](#)) will be registered. In addition, 200 IPF patients who have initiated or will initiate pirfenidone (classified as Group I, II and III, see [section 10.1](#)) at the same centers and during the same time frame will also be registered.

The medical records at the selected sites will be screened to enroll Group A and B patients in a retrospective manner. Group C patients will be enrolled prospectively. The first patient enrolled at a given site should be in the nintedanib group. Once a patient is enrolled into the nintedanib group, the

site team is suggested to enrol the next eligible patient, who has initiated/will be initiating pirfenidone at the same site in the pirfenidone group.

Patients will be registered by entering following necessary information in the electronic data capture (EDC) system. This information will be mandatory for registration:

- Demographics
- Pulmonary function tests at visit 1 and further visits [FVC, FVC % predicted, FEV1 (mL), FEV1 % predicted, DLCO] – Yes/No/Unknown. If yes specify the values with the dates.
- Family history
- Time since IPF diagnosis (date)
- Chest HRCT evaluation (UIP pattern, Possible UIP pattern, Inconsistent UIP pattern, emphysema)
- Surgical lung biopsy (yes/no/unknown) (UIP pattern, probable UIP pattern, possible UIP pattern, inconsistent with UIP or non-classifiable, not available)
- Previous history of acute exacerbation (Yes/ No/unknown)
- Vital signs and physical examination [Heart rate (beats per minute), blood pressure (systolic blood pressure, diastolic blood pressure) weight and height] - available/not available/unknown, value, date.
- Symptoms
- Known hepatic/renal impairment (yes/no/unknown)
- Comorbidities at visit 1 (yes/no/unknown, if yes specify)
- Bleeding and thrombotic risk (yes/no/unknown)
- Previous medications for IPF (yes/no/unknown, if yes specify)
- Co-medications [at visit 1 and further visits (whether used or not, unknown, start and stop date and dose)]
- Laboratory tests at visit 1 e.g. LFT (performed/not performed/unknown/Performed but missing value and value, date)]

End of registration:

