The patient registration at the selected centers will continue till 200 IPF patients treated with Nintedanib from the date of commercial availability of drug in India (23rd January 2017) are included; and their safety data are collected for at least 52 weeks or till the discontinuation of the drug, whichever is earlier. Baseline characteristics of 200 IPF patients treated with Pirfenidone at the same sites during the same period will also be collected.

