10.2.3 Discontinuation of the study by the sponsor

A log of all patients included into the active surveillance study will be maintained at participating sites.

Boehringer Ingelheim India Pvt Ltd reserves the right to discontinue the study overall or at a particular study site at any point in time for the following reasons:

- Emergence of any new information on the safety of Nintedanib which mandates the discontinuation of the study
- Violation of the protocol, or the contract by a study site or investigator, disturbing the appropriate conduct of the study

The site will be reimbursed for reasonable expenses incurred in case of study termination (except in case of the second reason).

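### Section 10.9 credits the design with enrolling all nintedanib initiators, but the enrolment sections neither require this nor keep the records needed to check it

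*Protocol*

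**What the plan says.** The protection is stated once, in protocol section 10.9: "The possible selection bias will be minimised by enrolling all patients who have initiated or will initiate nintedanib". The sentence goes on to name Groups A, B and C, the date of commercial availability (23 January 2017) and the selected centres.

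The sections that govern enrolment say the following:

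- **Target.** Section 10.1: "200 IPF patients treated with nintedanib per the Indian label will be enrolled in this active surveillance program". Section 10.5 gives the basis: "The sample size of 200 is as per the request from the regulatory agency".
- **Stopping.** Section 10.2.2.2 sets no calendar window: "It will end as soon as 200 patients are enrolled". The end-of-registration text in 10.2.2.3 agrees: "The patient registration at the selected centers will continue till 200 IPF patients treated with Nintedanib".
- **Choice of retrospective patients.** Section 10.2.2.3: "The medical records at the selected sites will be screened to enroll Group A and B patients in a retrospective manner". It states no order, starting point or completeness rule.
- **Only sequencing rule.** This concerns the pirfenidone group and is advisory: "site team is suggested to enrol the next eligible patient".
- **Log.** Section 10.2.3: "A log of all patients included into the active surveillance study will be maintained at participating sites".

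In the SAP, section 6.3 starts the Screened Set at a signed consent form.

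**The concern.** The surveillance exists to estimate how often ADRs and SAEs occur, and both primary outcomes are incidences in one followed cohort. Such estimates depend on who enters the cohort. Section 10.9 answers that question with complete enrolment at the centres, but nothing in the enrolment procedure makes enrolment complete or consecutive.

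This matters most for charts that already contain outcomes. Group A patients have stopped the drug and Group B patients are part-way through treatment, so events to date can be seen before a chart is picked. If that knowledge affects the choice, in either direction, the incidences shift. SAP section 6.5 states that no statistical model is involved, and no planned analysis would detect or correct such a shift. The report could then repeat a safeguard that cannot be demonstrated.

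**Working it through.** **1. No figure to reproduce.** The 200 is a regulatory request with no event rate, precision or power behind it. The check is therefore a comparison of passages, followed by an illustration.

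**2. Stated property against operative text.**

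| What enrolling all initiators needs | What the operative text provides |
|---|---|
| Every eligible initiator at a centre approached, or a consecutive series up to the cap | A total of 200 (10.1, 10.2.2.3, 10.5); stop at 200 (10.2.2.2) |
| An order for going through existing charts | Chart screening for Groups A and B, no order given (10.1, 10.2.2.3) |
| A count of eligible patients, including those not enrolled | A log of included patients (10.2.3); Screened Set from signed consent (SAP 6.3) |

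None of the three needs is met. Initiators who are never approached, or who decline, are not required to be counted anywhere.

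**3. Where outcomes are visible at selection.**

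- Group A: fully retrospective, so yes.
- Group B: yes for events up to participation, no for events afterwards.
- Group C: prospective, so no.
- Pirfenidone patients: not followed, baseline data only, so this mechanism does not apply.

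**4. Illustration of size.** All inputs here are assumed; the documents give none. Let the true SAE proportion among eligible initiators be 30%, and let patients with an SAE be *k* times as likely to be enrolled as those without.

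Observed proportion = 0.30*k* / (0.30*k* + 0.70)

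| *k* | Calculation | Observed, if all patients are affected | Observed, if half of those enrolled are Group C at 30% |
|---|---|---|---|
| 0.5 | 0.150 / 0.850 | 17.6% | (17.6 + 30) / 2 = 23.8% |
| 0.8 | 0.240 / 0.940 | 25.5% | (25.5 + 30) / 2 = 27.8% |
| 1 | 0.300 / 1.000 | 30.0% | 30.0% |
| 1.25 | 0.375 / 1.075 | 34.9% | (34.9 + 30) / 2 = 32.4% |
| 2 | 0.600 / 1.300 | 46.2% | (46.2 + 30) / 2 = 38.1% |

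For scale, the exact (Clopper-Pearson) 95% interval for 60 of 200 (30%) is 23.7% to 36.9%. With all patients affected, *k* of 0.8 or 1.25 stays inside that interval, and *k* of 0.5 or 2 falls outside it.

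**5. The same question from the missing denominator.** Let the enrolled risk be 30%, the share of eligible initiators passed over be *f*, and their risk relative to enrolled patients be *RR*.

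Enrolled risk minus all-initiator risk = −0.30 × *f* × (*RR* − 1)

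- *f* = 10%, *RR* = 1.25: −0.30 × 0.10 × 0.25 = −0.8 points.
- *f* = 20%, *RR* = 2: −0.30 × 0.20 × 1 = −6 points, close to the interval half-width of about 6.6 points.
- *f* = 50%, *RR* = 2: −0.30 × 0.50 × 1 = −15 points.

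An *RR* below 1 reverses the sign. Without a record of eligible patients not enrolled, *f* cannot be estimated.

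**The case against.** **Section 10.9 can be read as the instruction.** It is current protocol text, limited to the selected centres, and section 10.10.1 requires conduct in line with the protocol. On that reading sites enrol every eligible patient until the total reaches 200. The reading is possible, but 10.9 is a limitations paragraph, and neither 10.1 nor 10.2.2.3 repeats the instruction. Even if sites follow it, the required records would not show that they did.

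**The cap is not a bias.** This stands. A consecutive series stopped at 200 would be acceptable. A reader might infer that complete enrolment is impossible, but that assumes the centres have more than 200 eligible initiators, and the documents do not say so.

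**The denominator is not lost for good.** This also stands. Nothing forbids a fuller log, and section 10.10.1.3.2 gives monitors access to source records. The supportable statement is that the plan does not require the count to be kept.

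**The mechanism is narrow.** It excludes Group C and the pirfenidone patients. Group A may not reach the analysis at all: SAP section 6.1 lists only Groups B and C, and SAP section 6.3 requires signed consent, which the protocol does not ask of Group A. That mismatch is a separate point to reconcile and adds no weight here.

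**The baseline-data criterion is a weak filter.** Inclusion criterion 4 might look like a further source of selection. However, many of the fields accept an unknown or not-performed entry, and violation A1.4 in SAP section 6.2 removes nobody from any analysis set.

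**Part of the protocol is unseen.** The abstract (section 5) and flowchart are not in the public copy. What is said here about missing rules covers the body text only.

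**Conclusion.** The point holds as a mismatch between a stated safeguard and the procedure meant to deliver it. Section 10.9 claims enrolment of all initiators at the selected centres. The operative sections require 200 patients, set no order for the Group A and B charts, and require no record of eligible patients who were not enrolled. The defect is the combination of cap, missing order and missing denominator.

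A reader might go further and conclude that the incidences will be biased, or biased downwards. The documents do not support that. Selection on outcome is possible for Group A and for the pre-participation part of Group B, but it is not shown, and its direction is open. The range of 17.6% to 46.2% rests on an assumed 30% true proportion, on *k* between 0.5 and 2, and on all patients being affected. If half of those enrolled are in Group C, it narrows to 23.8% to 38.1%. Nor does outcome-dependent selection extend to the pirfenidone profile, where only baseline data are recorded.

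The estimates remain usable. The plan should be changed because a claim made to a regulator is currently unsupported and cannot be checked.

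**What to change.** 1. **Sections 10.1 and 10.2.2.3.** Have each site list its eligible nintedanib initiators since 23 January 2017 by start date and approach them consecutively until the overall total of 200 is reached. Use the same ordering for the pirfenidone list, in place of the present suggestion, so that the profile comparison rests on a defined series too.
2. **Section 10.2.3.** Extend the log to eligible patients not enrolled, de-identified and with the reason.
3. **SAP.** Report enrolled over eligible, by site and by group.
4. **Section 10.9.** State that enrolment is consecutive up to 200. If steps 1 and 2 are not adopted, state that not all initiators are necessarily enrolled and that selection bias is an uncontrolled limitation.

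The cost is protocol wording and some site paperwork, drawn from records that the sites already screen. The log of non-enrolled patients may also need ethics committee notification, since section 10.1 already makes Group A data collection and sharing subject to ethics approval. If enrolment is too far advanced for a consecutive approach, rewording 10.9 is the minimum.

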10.10 OTHER ASPECTS

10.10.1 Informed consent, data protection, study records

The active surveillance will be carried out in compliance with the protocol, and the latest revision of the Declaration of Helsinki, as well as the Guidelines for Good Pharmacoepidemiological Practice (GPP) from Epidemiological Society for Pharmacoepidemiology (ICPE), [REDACTED] guideline, Guideline on good pharmacovigilance practice, relevant BI SOPs and relevant local regulations.

Standard medical care (prophylactic, diagnostic and therapeutic procedures) remains the responsibility of the patient's treating physician.

The rights of the investigator and of the sponsor with regard to publication of the results of this active surveillance will be described in the contract. As a general rule, no results should be published prior to finalization of the Study Report.

10.10.1.1 Study approval, patient information, and informed consent

The review by Drug controller general of India (DCGI), Institutional Review Board (IRB) or Ethics Committee will be sought as per the institutional procedures before the start of this active surveillance program.

Prior to patient's participation in this active surveillance program, written informed consent must be obtained from each patient (or the patient's legally accepted representative) according to the regulatory and legal requirements of India (applicable for Group B/C and II/III patients). Each signature must be personally dated by each signatory and the informed consent and any additional patient-information form must be retained by the Investigator as part of the study records. A signed copy of the informed consent and any additional patient information must be given to each patient or the patient's legally accepted representative.

The Investigator must give a full explanation of this active surveillance program, regarding the collection of the safety data at specific time points to these participants. The Investigator obtains written consent of the patient's own free will with the informed consent form after confirming that the patient understands the contents. The Investigator must sign and date the informed consent form.

10.10.1.2 Data quality assurance

Automatic checks at data entry will reduce the error while entering data. A quality assurance audit/inspection of this active surveillance may be conducted by the sponsor, sponsor's designees, or by IRB/IEC or by regulatory authorities. The quality assurance auditor will have access to all medical records, the study related files and correspondence, and the informed consent documentation.

10.10.1.3 Records

Electronic data capture (EDC) system will be used to gather the data.

